**Group 2: NIV arm**

#1 NIV at 40% FiO2 for 3 minutes

#2 NIV at 70% FiO2 for 3 minutes

#3 NIV at 100% FiO2 for 3 minutes, the maximal reading at the end of this trial will be recorded, then the study subject will be allowed to rest until their EtO2 returns to their baseline, then they will be placed back on NIV at 100% FiO2, allowed to rise to the maximal reading of the previous step, then do a single breath exhaled EtO2 measurement

After each trial for #1 and #2 in each study arm, the study participants will be allowed to rest while breathing room air. Prior to the start of the next trial, each participant will perform a single breath EtO2 measurement to ensure they have returned to their baseline measurement. If the measurement is determined to be above their baseline, they will be allowed to rest until their single breath EtO2 measurement returns to its pre-intervention baseline. For trial #3 in each arm, the protocol will be followed as above so that the maximal reading can first be obtained to allow the completion of arm #3.

**Risks and Discomforts**

The risks to study participants would be no more than minimal risk. The most common risk to study participants would be discomfort from using the NRBm or NIV masks. Participants may experience claustrophobia or discomfort from the higher flows of oxygen and air. If participants cannot tolerate the NRBm or NIV mask, they can discontinue the study at any time by removing the NIV mask themselves or asking a study investigator to remove the mask.

The study's original PI and the author of this protocol ([name]) has designed and helped to execute a similar study at his last institution that was similar in design to this study. This study involved placing healthy volunteers on a NIV mask with a nasal cannula

underneath the mask. All study subjects (64 in total) were able to tolerate the full study protocol without any adverse effects. This study has been published in a peer-reviewed journal. The IRB approval letter designated the study as “no more than minimal risk” with an expedited review is included in the e-IRB submission as an appendix.

## **Randomization**

Study subjects will be randomized by computer to their initial study arm (NRBM or NIV). Study subjects will then be randomized by computer to the order of oxygen flows/FiO2 levels delivered by the NRBm or NIV mask, respectively.

## **Data collection and storage procedures**

All data will be collected on a standardized data collection form and entered into a secure database program (REDCAP) for data analysis. The PI, AI, and any study research personnel who assist with the study will have access to the database. Each subject will be assigned a subject number according to the order in which they were enrolled into the study. The data will be stored for a maximum of 3 years to ensure the ability to publish study results. After the data is stored for 3 years, it will be deleted. In addition, the study investigators will video record the screens displaying the EtO2 data to allow accurate data transcription. Once the data has been transcribed, these videos will be deleted. These videos will solely be focused on the video screen and will not capture the study subject’s face or any other identifying features. These videos will only be identified by the assigned study subject number and will not contain any other identifying information.

## **Participant selection**

This study will be conducted in healthy volunteers. Volunteers will be recruited from within the staff of the ED at Grady Memorial Hospital. We aim to enroll 104 participants- 52 in each study arm. Assuming a dropout rate of 10%, we will enroll a maximum of 116 patients. However, enrollment will terminate once 104 participants with a full data set have been enrolled.

### **Inclusion criteria (with justification in parentheses):**

- Adults 18 years of age and older who are able to consent on their own without a legal representative (ability to consent)
- Self-identified as being in good health (ensuring healthy volunteers)
- Grossly normal dentition as judged by study investigators (may affect NIV mask seal)
- No self-reported symptoms of upper respiratory infection or other infectious process (ensuring healthy volunteers)
- No history of severe pulmonary disease or asthma that requires daily use of an inhaler (ensuring healthy volunteers)
- Females participants only: Self-reported to not be pregnant at time of study enrollment (for protection of an unborn child)

**Exclusion criteria:**

- Participant does not agree to study enrollment
- Participant cannot tolerate the entire course of non-invasive ventilation required to complete the study.
- Participant does not agree to the video recording of the oxygen monitor to ensure proper data transcription

Study subjects will be recruited from within the Department of Emergency Medicine at Grady Memorial Hospital and Emory University Hospital Midtown. Study participants will be drawn from a pool that will include nursing staff, paramedical staff, students, residents, and attending physicians.

Study subjects will be assessed for inclusion or exclusion criteria prior to starting the study. Study subjects will provide written informed consent after the study procedures have been explained to them and any questions are answered. No personally identifiable health information will be collected during study enrollment.

If a study subject wants to withdrawal from the study they can do so by notifying the study investigators at any time. If a study subject chooses to withdrawal, they will most likely do so due to intolerance of the NRB or NIV mask. If this occurs, they can remove the NRB or NIV mask themselves or request that a study investigator remove the NIV mask for them. The option to remove the mask themselves or request that a study investigator remove the mask for them will be made clear during the process of written informed consent.

**Informed consent process**

Each study participant will provide written informed consent for the study. After screening for inclusion or exclusion criteria, a study investigator will explain the study procedures in plain language. Study participants will then be allowed to ask any questions to be answered by the study investigator. If the study participant agrees to enrollment, they will be provided with the written informed consent document and be given sufficient time to read the document and ask any additional questions. The study procedures will not be implemented until the study participant signs the informed consent document.

A HIPAA authorization will be included in the text of the consent document for the study.

For student or resident participation, participation or non-participation will not have any effect on any grading or evaluation that they may receive during their rotation or training. For all other participants, participation or non-participation will not have any affect on any employee evaluation, salary, compensation, or continued employment with Grady Health System or Emory University.

In addition, no students or other trainees will be approached face to face for recruitment by the study personnel or their clinical supervisors. They will also not participate in the study during their clinical shifts and they will not be specifically targeted for enrollment. Students and other trainees will be recruited in a general fashion via emails to the department of emergency medicine and flyers placed in public areas of Grady Hospital and Emory University Hospital Midtown.

## **Study participant compensation**

Study subjects will be compensated with a \$20 Amazon Gift Card for their time once they are deemed to be eligible to participate in the study and have provided written informed consent. This study is anticipated to take approximately 45-60 minutes of the study subject's time to allow for written informed consent and all the study trial activities. If they choose to withdrawal prior to full study completion, they will keep the \$20 gift card.

## **Statistical Analysis:**

## **Power calculation**

The study will be sufficiently powered to detect a 5% difference in ETO2. Five percent was chosen because it equates to approximately 30 extra seconds of safe apnea time in an 80 kilogram male (5% X 2,400 ml/O2 consumption at 250 ml/min). Based on a previous studies with similar study designs, we estimated that the standard deviation of ETO2 would be approximately 6.8%. Because six tests will be conducted, findings will be considered significant at the 0.0085 level (Sidak-corrected p value). These values were used to estimate the sample size required to achieve 80% power using Monte Carlo Simulations (10,000 samples) implemented in R v3.4.1. This analysis returned a total sample size of 104 (52 per arm). In order to account for an anticipated dropout rate of 10%, 116 participants will be enrolled. However, study enrollment will be terminated once 104 study subjects with complete data sets have been enrolled.

If a study participant cannot complete the entire protocol, their data will be excluded from the data analysis.

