Real Time Assessment of Pre-oxygenation Utilizing End-tidal Oxygen Measurements versus Single Breath End-Tidal Oxygen Measurements in Healthy Volunteers

Short Title: Pre-oxygenation with Real Time End-tidal Oxygen Measurements versus Single Breath Measurements

Principal Investigator: [name]

Sponsors: None

Protocol Version 6  
March 20, 2025

NCT03840486

1. External (non-Emory) Collaborators: Not applicable
2. Precis/Abstract: A brief (usually 400 words or fewer) description of the study objectives, population, design, and outcome measures

Patients in the Emergency Department (ED) undergoing Rapid Sequence Intubation (RSI) are at risk for serious morbidity and mortality. In order to provide oxygen during the apneic period, it is common practice to provide pre-oxygenation prior to the start of the procedure with high flows of oxygen. Different methods of pre-oxygenation have been studied by taking a single breath end-tidal oxygen (EtO2) measurement with higher levels indicating more complete pre-oxygenation. However, there has not been any research examining methods of determining the quality of pre-oxygenation in real time.

This study examines the performance of a nasal cannula EtO2 measurement as compared to the gold standard of single breath end-tidal oxygen measurements in healthy volunteers. Study subjects will be placed on either a NRBM at different flow rates (15 LPM, 35 LPM, or Flush rate at 55 LPM) or a non-invasive ventilator facemask at various fractions of inspired oxygen levels (40%, 70% and 100%) for separate trials of 3 minutes at each flow rate or FiO2. At the end of each intervention, study subjects will perform a single breath end-tidal oxygen measurement by exhaling fully into a tube attached to an EtO2 sensor. In addition, a fourth trial arm will be done for both the NRBM and the NIV subjects that will correlate maximal readings from the real time EtO2 nasal cannula at the moment those maximal readings are obtained. The primary outcome will be the degree of correlation between real time EtO2 measurements (at the end of the three minute trial) and a single breath end-tidal oxygen measurement as measured by the k correlation coefficient, as measured for each trial. The secondary outcome will be the correlation of EtO2 between the nasal cannula sensor and the single breath sensor once stabilized at maximal readings.

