## **Introduction**

We hypothesize that end-tidal oxygen (EtO2) could be continuously and reliably measured using a nasal cannula with a gas sampling line that is typically used to measure end-tidal CO2 (EtCO2) during pre-oxygenation in healthy volunteers. However, it is possible that high flows of oxygen that would be typically required for pre-oxygenation could distort patient measurements when placed underneath the oxygen mask. To our knowledge, no studies have examined this technique.

Use of the EtO2 real time reading from a nasal cannula could lead to improved pre-oxygenation for ED patients undergoing RSI by allowing clinicians to gauge the completeness of pre-oxygenation prior to starting the intubation procedure. Clinically, if a patient has a low EtO2 or ORI reading, this could prompt clinicians to delay the procedure until the patient can be better pre-oxygenated. This could lead to improved patient safety by decreasing the incidence of hypoxia during the intubation procedure that can lead to significant morbidity and mortality. Conversely, if the EtO2 is already at 90% or greater, the clinician may be able to start the intubation procedure sooner and not delay other critical interventions while waiting to further pre-oxygenate the patient.

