### **3. Objectives:**

Primary Objective: In healthy volunteers, how well does a real time nasal cannula EtO2 sensor correlate with a single breath exhaled EtO2 measurement?

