### **4. Study design and methods:**

#### **Study Procedure**

After screening procedures, participants will be asked to self report age, gender, height, and weight. Each participant will then perform a single breath EtO2 measurement to determine their own individual room air EtO2 measurement. They will also have a baseline measurement taken by the EtO2 nasal cannula sensor. Subjects will then be fitted for an appropriately sized non-invasive ventilator mask. Prior to the start of the study procedure, a nasal cannula EtO2 sensor will be placed on the participant's face with the non-invasive mask overlying the sensor. Participants will be randomized into each study arm after enrollment: the NRBM arm and the

NIV arm. Each participant will participate in the following treatment sequence. In addition to the study arm allocation, participants will be randomized to the order of their treatment sequence. After each treatment is completed, the participant will perform a single breath exhalation into a standard FeO2 sensor.

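### The stated 80% power is for a 5-point difference in EtO2 in an unnamed comparison; the primary per-trial correlation has no stated precision and, depending on the undefined coefficient, may not register a constant offset between sensors

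*Combined protocol and SAP*

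**What the plan says.** The Precis/Abstract (section 2) defines the main result: "The primary outcome will be the degree of correlation between real time" EtO2 and the single-breath measurement, "as measured by the k correlation coefficient, as measured for each trial". The coefficient *k* is not defined anywhere. The secondary outcome is of the same kind: "The secondary outcome will be the correlation of" EtO2 between the two sensors at maximal readings. The Objectives section asks the same question: "In healthy volunteers, how well does a real time nasal cannula" sensor correlate with the single-breath value?

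Both readings come from the same person. Under Study Procedure, the cannula sensor is worn beneath the mask, and "After each treatment is completed, the participant will perform a single breath exhalation into a standard" sensor.

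The only power statement is in the Power calculation section: "The study will be sufficiently powered to detect a 5% difference in" EtO2. Its inputs are an SD of EtO2 of about 6.8%, a Sidak-corrected level of 0.0085 for six tests, 80% power by Monte Carlo simulation, and a resulting 104 participants (52 per arm). It does not say which measurements are compared, which test was simulated or what the six tests are. Apart from this section, which also covers exclusions, Statistical Analysis contains only Missing Data.

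The Introduction gives two reasons why the absolute level of the cannula reading matters. It warns that "high flows of oxygen that would be typically required for pre-oxygenation could distort patient measurements" under the mask. It also describes acting on the number itself: if EtO2 "is already at 90% or greater, the clinician may be able to start the intubation procedure sooner".

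**The concern.** A reader will naturally take the 80% as power for the primary result. It belongs to a difference in EtO2, and a correlation is a different quantity with its own precision, which the plan does not give.

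The second issue is what the primary result can show. The intended use is to act on an absolute reading, and the Introduction foresees distortion of that reading. Ordinary correlation coefficients measure whether two readings rise and fall together, not whether they are equal. If *k* is one of these, the primary result could look good while the cannula reads consistently too high or too low. No analysis of mean bias or agreement is explicitly described.

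**Working it through.** **Inputs from the Power calculation section.** Difference 5 points; SD of EtO2 6.8; level 0.0085; power 80%; 52 per arm. Tests are assumed two-sided, because the plan does not say.

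**1. The plan's own figures.**
- Sidak level for six tests: 1 − 0.95^(1/6) = 0.00851, which matches 0.0085.
- Enrolment: 104 / 0.9 = 115.6, rounded up to 116, which matches.
- Sample size by two-sample t-test (noncentral t): power is 79.6% at 46 per arm, 80.7% at 47 and 85.4% at 52. At n = 52 the noncentrality is 5 / (6.8 × √(2/52)) = 3.75, against a critical t of 2.68 on 102 df.

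The 52 per arm is thus not reproduced exactly; the inputs need 47. The stated number is mildly conservative for this test. No correlation enters the calculation.

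**2. A paired reading of the power statement.** Suppose the 5 points are cannula versus single breath within one setting. With both SDs equal to 6.8 (an assumption) and between-sensor correlation ρ, SDdiff = 6.8 × √(2(1 − ρ)). The table uses n = 52 and critical t(51) = 2.738. Half-width is 2.738 × SDdiff / √52, and limits of agreement are ±1.96 × SDdiff.

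| ρ | SDdiff | Power for 5 points | 99.15% CI half-width | Limits of agreement around the mean difference |
|---|---|---|---|---|
| 0 | 9.62 | 83.9% | 3.7 | ±18.8 |
| 0.5 | 6.80 | 99.4% | 2.6 | ±13.3 |
| 0.8 | 4.30 | >99.9% | 1.6 | ±8.4 |
| 0.9 | 3.04 | >99.9% | 1.2 | ±6.0 |

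Power falls below 80% once SDdiff exceeds about 10.0. This can happen if the cannula is the noisier sensor. With an assumed cannula SD of 10 against 6.8 and ρ = 0.3, SDdiff = √(6.8² + 10² − 2 × 0.3 × 6.8 × 10) = 10.27, and power is 77.6%.

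**3. Precision of the primary correlation.** Assume Pearson and one correlation per trial with n = 52. Fisher's z has standard error 1/√(52 − 3) = 1/7, so the interval is tanh(atanh(r) ± c/7), with c = 1.960 for 95% and 2.632 for 99.15%.

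| Observed r | atanh(r) | 95% CI | 99.15% CI |
|---|---|---|---|
| 0.80 | 1.099 | 0.67 to 0.88 | 0.62 to 0.90 |
| 0.90 | 1.472 | 0.83 to 0.94 | 0.80 to 0.95 |

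**4. Effect of a constant offset.** Adding a constant to one sensor leaves Pearson, Spearman and Kendall coefficients unchanged. Lin's concordance coefficient with equal SDs is 2 × r × SD² / (2 × SD² + offset²). With r = 0.90, SD² = 6.8² = 46.24 and an offset of 5, it is 2 × 0.90 × 46.24 / (92.48 + 25) = 0.71. With no offset it equals r, 0.90.

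**The case against.** The strongest reply is that the plan may already contain the offset test. There are three numbered trials in each of two arms, so six tests fits one cannula-versus-single-breath comparison per trial. If those compare means, they address offset, and with a 5-point target. This stands as a plausible reading, and the point is limited accordingly. It does not remove the point: the plan names no comparison, and such a test would still not be the stated primary outcome.

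Second, *k* may be a concordance or kappa-type statistic, which an offset would lower. That also stands. The plan's repeated use of the word correlation suggests an ordinary coefficient but does not settle it, so the offset argument is conditional.

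Third, an objective that asks how well two sensors correlate needs no hypothesis-test power. Agreed; but it then needs a stated precision, and none is given.

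Three stronger readings are tempting and are not supported:
- A reader might infer that the trial is too small. On the stated inputs it is not. A shortfall for a paired test requires an SDdiff above about 10, and the documents give no such figure.
- A reader might infer that offset is certainly left unexamined. With the six tests unnamed, the documents do not establish that.
- A reader might infer that a correlation merely significant against zero would be taken as proof that the sensors are interchangeable. The plan states no test against zero and makes no such claim.

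**Conclusion.** The point holds in a limited form and should be fixed. The mismatch between power statement and primary outcome, and the absence of any stated precision for that outcome, follow directly from the text. Both stand whatever *k* proves to be.

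The offset part is conditional on *k* being Pearson, Spearman or Kendall and on the six tests not already being mean comparisons of the two sensors. Where both conditions hold, a 5-point bias, the size that the plan itself treats as worth detecting, would leave the primary result untouched.

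The finding that the sample is adequate is also conditional. It is 85.4% power for a two-sample t-test on the stated inputs, and at least 83.9% for a paired t-test if both SDs are 6.8 and the between-sensor correlation is 0 or more. The precision figures for r assume Pearson and 52 complete participants per trial. The defect is in what the plan claims and specifies; enrolment and data collection are not at fault.

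**What to change.** Keep enrolment as planned and change three things.

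1. In Power calculation, state that the 80% concerns a 5-point difference in mean EtO2 and is not power for the primary correlation. Name the simulated test and list the six tests.
2. In the Precis and in Statistical Analysis, name the coefficient now called *k* and state its expected precision at one declared confidence level. If it is Pearson, the sentence could read: With 52 participants per trial, an observed r of 0.80 has a 95% CI of 0.67 to 0.88, and an r of 0.90 has a 95% CI of 0.83 to 0.94. If the corrected level is to apply, use the 99.15% intervals, 0.62 to 0.90 and 0.80 to 0.95. Recompute for any other coefficient.
3. For each setting, pre-specify the mean paired difference (cannula minus single breath) with its CI at the declared level; if the six tests already are this comparison, say so explicitly. Report limits of agreement descriptively, with no imposed margin. At the 99.15% level the expected half-width is 1.6 points at an assumed SDdiff of 4.3 and 2.6 points at 6.8.

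The cost is some rewording and one small analysis of readings already being collected. The drawback is that the paired-difference precision rests on an assumed SDdiff and must be labelled as such.

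### If the six planned tests are tests of the correlation, p < 0.0085 cannot show whether the cannula can stand in for the single breath, and no agreement analysis is prespecified

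*Combined protocol and SAP*

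**What the plan says.** The Precis/Abstract makes the primary outcome the degree of correlation between the real-time cannula reading at three minutes and the single-breath reading, "as measured by the k correlation coefficient, as measured for each trial". The primary objective asks how well the two correlate. The Introduction hypothesizes that the cannula can measure EtO2 reliably, and the Precis calls the single breath the gold standard.

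The Statistical Analysis section contains a power calculation and a missing-data paragraph. The power calculation concerns a difference, not a correlation: "The study will be sufficiently powered to detect a 5% difference in" EtO2, with an SD that "would be approximately 6.8"%, 80% power and 52 per arm. Its rule for judging results is "Because six tests will be conducted, findings will be considered significant at the 0.0085 level (Sidak-corrected p value").

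The documents do not list the six tests or give their null hypotheses. They set no minimum correlation, limit on bias, limits of agreement or equivalence margin.

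**The concern.** Whether one device can replace another is a question of agreement: how far apart the two readings are in the same person. Neither plausible use of the 0.0085 threshold on the two sensors answers it.

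- **Test of the correlation.** The natural null is zero correlation. Two sensors sampling the same lungs should reject it even if one is imprecise. Correlation also ignores a constant offset. That matters here because the Introduction itself warns that high oxygen flow under the mask could distort the cannula reading, and a uniform distortion leaves r unchanged.
- **Test of the mean difference between sensors.** The result that favours the cannula is a non-significant one. Failing to find a difference is not evidence of agreement, and a stricter level makes a real offset easier to miss.

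The plan values 5 points of EtO2 at about 30 seconds of safe apnea time, so errors of that size matter by its own yardstick. With no other criterion in place, the basis for judging cannula performance would have to be chosen after the data are seen.

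**Working it through.** **Inputs from the Power calculation section:** per-test level 0.0085, six tests, difference of 5 points, SD 6.8 points, 52 per arm.

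**Assumptions, because the documents are silent:** one test per setting (3 settings × 2 arms, n = 52 each), two-sided, Pearson r, and SD 6.8 for both sensors. The plan gives no SD of paired differences, so a range is shown.

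**The plan's own figures.** The Sidak level is 1 − 0.95^(1/6) = 0.0085, which reproduces. The 52 per arm does not follow from standard formulas. A two-sample, two-sided t-test needs 47 per arm for 80% power, and 52 per arm gives 85%. The plan used simulation that it does not describe, and the difference errs on the large side. The checks below need only n = 52 and the 0.0085 level.

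**Tests of the correlation**

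1. Critical value: t (50 df, two-sided 0.0085) = 2.740, so r = 2.740/√(2.740² + 50) = 0.361, and r² = 0.13.
2. Range for other readings: 0.330 one-sided, 0.257 if all 104 are pooled, about 0.25 for Kendall's tau.
3. Chance of significance at true r = 0.5 (Fisher z): Φ(0.549 × √49 − 2.63) = 0.89.
4. Agreement at r = 0.5: SD of differences = 6.8 × √(2 × (1 − 0.5)) = 6.8. Limits of agreement are ±1.96 × 6.8 = ±13.3 points around any bias. With no bias, P(|difference| > 5) = 2 × (1 − Φ(5/6.8)) = 0.46.
5. At the critical value itself (r = 0.361), the SD of differences is 7.7 and the limits are about ±15 points.

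**Tests of the paired difference.** With n = 52 and noncentral t, the chance of missing a true offset is:

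| Correlation between sensors | SD of differences | True offset | Missed at 0.05 | Missed at 0.0085 |
|---|---|---|---|---|
| 0.5 | 6.8 | 3 points | 12% | 33% |
| 0.5 | 6.8 | 5 points | 0.06% | 0.6% |
| 0 | 9.6 | 5 points | 4% | 16% |

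The 9.6 is 6.8 × √2.

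**Would an interval for the mean difference be enough?** Take a rule that passes the cannula if the 90% confidence interval for the mean difference lies within ±5 points. An unbiased cannula wholly uncorrelated with the single breath (SD of differences 9.6) would pass about 96% of the time. Yet 2 × (1 − Φ(5/9.6)) = 60% of its readings would miss by more than 5 points. A rule on the mean alone does not deal with imprecision.

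**The case against.** **The plan does not treat p < 0.0085 as proof of accuracy.** A reader might infer that it does, since it offers no other threshold. But the outcome is a degree of correlation and the objective asks how well the sensors correlate, and both are estimation questions. This stands. The fault is a missing agreement criterion, not a false claim in the text.

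**The six tests may not compare the sensors.** The 5 points are justified by extra apnea time, and the SD comes from studies that the Background describes as comparing oxygenation strategies. Three settings in each of two arms also give six within-arm pairwise comparisons. On that reading a non-significant result says nothing in the cannula's favour, and the Sidak correction is ordinary. This stands too, so a reader who infers that the correction is perverse goes beyond the documents. It remains true that the tests are undefined, and on that reading the primary outcome has no decision rule.

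**The penalty for a 5-point offset is easily exaggerated.** A two-sample calculation with 52 per arm gives a 14.6% miss rate at 0.0085 against 4.0% at 0.05. Both sensors are read on the same person, so that calculation does not apply. On the paired basis, with sensors correlated at 0.5 or more, the miss rate is at most 0.6%.

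**The coefficient is undefined.** If k denotes a kappa or concordance measure, the 0.361 does not carry over. No success threshold is stated for such a measure either.

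**Conclusion.** The point holds in conditional form. If the six tests concern the primary correlation, the 0.0085 threshold is met at |r| above 0.361. It would be met 89% of the time at a true r of 0.5, where limits of agreement are about ±13.3 points and 46% of readings miss by more than 5. If they are paired sensor differences, non-significance does not show agreement. The stricter level then mainly hides offsets below 5 points, unless the sensors are nearly uncorrelated. In neither case would following the plan as written show whether the cannula can stand in for the single breath.

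The figures rest on Pearson r, two-sided tests, 52 per setting and a common SD of 6.8. The documents state only the last two numbers, and the 6.8 is not assigned to either sensor. The data to be collected can answer the question, so this is a cheap improvement and not a flaw in the design.

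**What to change.** In the Power calculation section, or in a new analysis paragraph beside it:

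1. State what each of the six tests compares, its null hypothesis and whether it is two-sided.
2. Make an agreement analysis at each setting the basis for any claim about cannula performance. Report the mean paired cannula-minus-single-breath difference with its confidence interval, and 95% limits of agreement with their confidence intervals. Read both against the plan's own 5-point important difference.
3. Report the correlation as an estimate with a confidence interval, not as a test against zero.
4. Do not call the cannula accurate on the mean-difference interval alone.

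This costs some protocol wording and a little more analysis, on data already being collected. With 52 per setting and an SD of differences of 6.8, each limit of agreement would be known to about ±1.96 × 6.8 × √(3/52) = ±3.2 points.

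The downside is that a favourable claim becomes harder to make. With no bias, estimated limits inside ±5 points need an SD of differences of at most 5/1.96 = 2.55. With SD 6.8 for both sensors, that means a correlation of about 1 − (2.55/6.8)²/2 = 0.93 or more.

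### Optional efficiency gain: the single-step Sidak level of 0.0085 for all six tests is valid, but Holm-Sidak step-down keeps the same 5% family-wise error and never rejects less

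*Combined protocol and SAP*

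**What the plan says.** The Power calculation section of the combined protocol and SAP gives one decision rule for all six tests: "Because six tests will be conducted, findings will be considered significant at the 0.0085 level (Sidak-corrected p value". The sentence governs which findings count as significant, and the same level then enters the sizing: "These values were used to estimate the sample size required to achieve 80% power using Monte Carlo Simulations (10,000 samples) implemented in R v3.4.1". The sizing inputs are a 5-point difference in EtO2 and an SD that "would be approximately 6.8" percentage points, and the result is 104 volunteers, 52 per arm. No step-down or hierarchical rule, and none that uses the correlation between tests, appears elsewhere.

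The six tests are not listed. The Precis/Abstract describes the primary outcome "as measured by the k correlation coefficient, as measured for each trial", and each arm has three 3-minute settings, so three tests in each of two arms is the natural inference. Under Study Procedure, "Each participant will participate in the following treatment sequence", so tests within an arm use the same volunteers.

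**The concern.** Single-step Sidak charges every test the full six-fold penalty. When five hypotheses have already been rejected, the sixth is still held to 0.0085, although only one hypothesis then remains that could be falsely rejected. Step-down procedures remove this penalty as rejections accumulate, and the 5% limit on family-wise error stays the same.

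At stake is which results can be declared. A test with a p-value above 0.0085 but below its step-down threshold would be reported as non-significant, although control of the family-wise error does not require that.

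**Working it through.** **1. The plan's threshold.** 1 − (1 − 0.05)^(1/6) = 0.00851, which matches the stated 0.0085. Six independent tests at 0.0085 give a family-wise error of 1 − (1 − 0.0085)^6 = 0.0499. The single-step rule does what it claims.

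**2. Step-down thresholds.** The thresholds are 1 − 0.95^(1/k), where k is the number of hypotheses not yet rejected:

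| k | 6 | 5 | 4 | 3 | 2 | 1 |
|---|---|---|---|---|---|---|
| threshold | 0.0085 | 0.0102 | 0.0127 | 0.0170 | 0.0253 | 0.05 |

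The first threshold equals the plan's level and the later ones are larger. Every single-step rejection is therefore also a step-down rejection.

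**3. Gain if single-step power is exactly 80% per test.** Assumptions, because the plan does not state these points: two-sided tests, normal statistics, two independent blocks of three tests, and within-arm correlation of 0 to 0.8. The mean of each real effect's statistic is set to z(1 − 0.00851/2) + z(0.80) = 2.631 + 0.842 = 3.473. Simulated average power per real effect, with 80% under single-step:

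| Real effects | Holm-Sidak gain (points) |
|---|---|
| six | 11.0 / 9.9 / 8.9 at correlation 0 / 0.5 / 0.8 |
| five | 6.4 to 7.5 |
| four | 4.4 to 5.0 |
| three | about 2 to 3 |
| two | about 1.4 or less |
| one | under 0.1 |

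With six real effects, the chance that all six are significant rises from 26 / 38 / 47% to 65 / 70 / 75% at correlation 0 / 0.5 / 0.8. Step-down lost no rejection in any replicate.

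**4. Family-wise error.** With no real effects it is about 5.0 / 4.6 / 3.7% at correlation 0 / 0.5 / 0.8, and the same for both procedures. With three true nulls, single-step uses 1.9 to 2.5% and step-down 3.3 to 4.4%. In all mixed cases step-down stayed at or below 5% within simulation error.

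**5. Baseline power at the planned size.** The plan's 52 per arm does not reproduce from the stated inputs. The normal formula gives n = 2 × (2.631 + 0.842)² × (6.8/5)² = 44.6, so 45 per arm. A two-sample t-test needs 47, a Mann-Whitney test about 49, and a paired t-test with uncorrelated readings 49. The test behind the plan's simulation is not named. These variants give about 83 to 87% power at 52 per arm, which leaves less room for a gain. With six real 5-point differences and 52 per arm:

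| Test (assumed) | Single-step power | Gain (points) |
|---|---|---|
| two-sample t | 85.4% | 7.8 to 9.4 |
| paired t, readings uncorrelated | 83.9% | 8.4 to 10.2 |
| paired t, correlation 0.2 | about 92% | 4.9 to 5.9 |
| paired t, correlation 0.5 | 99.4% | about 0.6 |

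**6. If the tests are of the correlation itself.** For zero correlation against an assumed true value, with Fisher's z and n = 52, power is Φ(√49 × atanh(r) − 2.631). At r = 0.5 this is Φ(7 × 0.549 − 2.631) = 89%. At 0.6 and 0.7 it is 98.7% and 99.97%. With all six real, step-down adds about 7, 1 and 0.03 points.

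**The case against.** Single-step Sidak is valid and prespecified, and it has matching simultaneous confidence intervals, which matter in a comparison of measurement methods. All of that stands. A result declared only by the step-down rule has p above 0.0085, so a 99.15% interval from the same test would include zero. This costs some clarity of presentation but leaves error control intact.

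A reader might infer that the plan gives up about 10 points of power on every test. The documents do not support that. The figure needs all six effects to be real and a baseline of 80%. The plan gives its 80% without saying that it applies to each test, and the stated inputs point to somewhat higher power. If the tests compare cannula with single breath, six real 5-point differences would also mean disagreement at every setting, which is contrary to the hypothesis in the Introduction. If the methods agree, few differences are real and the gain is near zero.

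A reader might also infer that the shared volunteers cause the loss. They do not. Holm-Sidak makes no use of the correlation, and within-arm correlation lowers its gain from 11 to about 9 points. Shared volunteers only require a procedure that is valid under correlation, and this one is.

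Finally, the six tests are not itemised, and the power statement concerns a mean difference while the primary outcome is a correlation. Those gaps matter more and should be settled first. They limit what can be said about the size of the gain. They do not change the fact that step-down keeps every single-step rejection.

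**Conclusion.** The point holds as an optional efficiency gain. The plan's rule is correct but uniformly less powerful than an alternative with the same 5% family-wise guarantee. The plausible gain in average power per test runs from about 0 to 11 points, and where it falls depends on the number of real effects and on baseline power. The upper end is a best case.

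The guarantee rests on two-sided tests with jointly normal statistics, and it then holds for any correlation. The sizes rest on further assumptions: three tests per arm, two-sidedness, within-arm correlation of 0 to 0.8, and the test types tried above. None of these is stated in the documents. A reading that the 0.0085 rule is an error, or that it inflates or fails to control the type I error, would be wrong.

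**What to change.** Before any analysis, replace the fixed significance rule in the Power calculation section with Holm-Sidak step-down. Order the six p-values from smallest to largest, compare them in turn with 0.0085, 0.0102, 0.0127, 0.0170, 0.0253 and 0.05, and stop at the first that fails. Report adjusted p-values. Keep 0.0085 in the sample-size statement as the worst-case threshold, so that the power stated at that level becomes a lower bound. List the six tests in the same place, because any multiplicity rule needs a defined family.

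The cost is one sentence of analysis text plus the list of tests. Sample size, study procedures and the family-wise error limit do not change. If 99.15% single-step intervals are reported alongside, add a note that they do not correspond exactly to the step-down decisions and may include zero for a result declared significant.
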